### **Secondary Endpoint Analysis**

The analyses for the time-to-event secondary endpoints will be similar to those outlined for the primary endpoint using the time from randomization through the first occurrence of any component of a specific secondary endpoint (or censoring) as the response variable, and assessing group differences using the Cox proportional hazards model. The effect of the chelation treatment strategy vs. placebo chelation on these time-to-event secondary endpoints will be summarized using hazard ratios (with associated confidence intervals) computed from the Cox model. Kaplan-Meier curves will be constructed to display the cumulative event rates of the treatment groups.

To test the individual treatment strategies against the placebo chelation – placebo OMVM group, we will add three indicator variables to the Cox proportional hazards model described above.

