1.1 Study Design

The Trial to Assess Chelation Therapy 2 (TACT2) is a randomized, double blinded, placebo-controlled 2x2 factorial clinical trial. The study treatments are edetate disodium-based chelation (weekly infusion for 40 weeks) and high-dose oral multivitamins and multi-minerals (OMVM) (twice daily for up to 5 years). Subjects with diabetes mellitus with a prior myocardial infarction (MI) are recruited from participating sites in the US and Canada and randomized in a 1:1:1:1 fashion to 4 groups:

- i. Active chelation + active OMVM
- ii. Active chelation + placebo OMVM
- iii. Placebo chelation + active OMVM
- iv. Placebo chelation + placebo OMVM.

Patients will be followed for clinical events until the earlier of database lock or five years from randomization. Clinical outcomes will be collected by study sites at each infusion visit and by the DCRI Call Center at month 6 and 12, and every 4 months afterwards with the last assessment at month 60.

TACT2 is an event driven trial with a plan to continue until at least 282 primary endpoint events are identified. The original planned sample size was 1200 participants. The sample size was later modified to 1100. The final enrollment is 1000, but with an increased follow-up time to preserve statistical power. More details on sample size and power calculation are included later in the SAP.

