Secondary Objective / mITT	Time from randomization to the first occurrence of the secondary composite endpoint of cardiovascular mortality, MI, or stroke	Cause specific hazard ratio estimate based on a cause-specific Cox proportional hazards model.	All positively adjudicated endpoint events post-randomization except those occurring after withdrawal of consent or ICF expiration date. Non-CV death or undetermined cause of death is considered a competing risk. Among subjects experiencing competing risk (non-CV death or undetermined death is a competing risk of CV death or MI/stroke if a subject died without having any	Among subjects not experiencing endpoint of interest or competing event: Censoring date = min(date withdraw consent, date of last contact with patient/proxy where event status was assessed) *Date of last contact defined in 1 st row, 5 th column (primary endpoint)

			
of these events beforehand):
 
Event date = non-CV or undetermined death date;
	
Secondary Objective / mITT	Time from randomization to all-cause mortality	Hazard ratio estimate based on a Cox proportional hazards model.	
All deaths post-randomization (including adjudicated deaths obtained from the NDI search)
 
A death date after withdrawn consent or ICF expiration (obtained from public data source) is considered an event.
	
Among subjects who are alive:
 
Censoring date = (date last known alive)
 
Date of last known alive defined as:
 
If the last contact occurred during the study infusion phase - use last infusion visit date.
 
If last contact occurred during call center follow up period – use ‘complete’/‘incomplete’ status date by patient/proxy or (‘not done’ status date where source = patient) or last alive date from Call Center where death status was assessed.

Secondary Objective / mITT	Total number of SAE and percentage of patients experiencing at least 1 SAE.	Number and proportions by treatment group. Confidence intervals will be based on the Miettinen-Nurminen method.	Randomization to min(withdraw consent, 30 days post final infusion)	N/A

Sensitivity Analysis of the Primary Outcome / Bayesian analysis using TACT results as one of the priors / mITT	*Same as primary analysis	Treatment effect mean posterior hazard ratio based on a Bayesian time to event model	*Same as primary analysis	*Same as primary analysis

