3.2.1 Primary Analysis

The primary objective is to determine if the chelation-based strategy increases the time to composite endpoint compared with the placebo chelation strategy. The primary composite endpoint will be analyzed using a Cox proportional hazards regression model of time from randomization to the first occurrence of all-cause mortality, MI, stroke, coronary revascularization, or hospitalization for unstable angina.

The primary analysis will be based on a Cox model which includes indicator variables for the active chelation as the primary variable of interest and active OMVM groups, age, sex, and baseline insulin use as covariates. Age will be included in the model in the form of cubic splines using three knots at 10th, 50th, and 90th percentiles. Two separate manuscripts will explore the effect of active OMVM and the effects of chelation by OMVM.

The chelation treatment effect will be summarized using hazard ratios and associated 95% CIs. A hazard ratio of < 1 would suggest a benefit for the chelation-based therapy. Kaplan Meier survival estimates will be constructed based on the time from randomization to the first

primary event occurrence. Events occurring after withdrawal of consent or informed consent expiration will be censored.

The OMVM treatment effect from the Cox model will be estimated using the Cox model described above. A hazard ratio of < 1 would suggest a benefit for OMVM treatment. Given the focus on chelation therapy, the interpretation of the OMVM treatment effect will be considered exploratory. A full set of analyses of the 2x2 design will be reported in a separate manuscript.

Four interim analyses were conducted at 25%, 40%, 60%, and 80% of expected information using a Haybittle-Peto-type boundary for efficacy (i.e. $p \leq 0.001$, $Z=3$). For this reason, the adjusted two-sided significance level for the final analysis is 0.05 (i.e., the corresponding critical value, $Z = -1.96$).

Formal statistical hypothesis testing will follow a hierarchy based on statistical significance of the prior endpoint. If the prior endpoint is statistically significant at the 0.05 level, the next endpoint's p-value will be tested for significance. The outcome hierarchy will be evaluated as follows:

- 1) Primary composite outcome
- 2) Secondary all-cause mortality outcome (with conservative censoring)
- 3) Secondary composite outcome of cardiovascular mortality, MI, or stroke

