3.3.2 Time to Event Analysis of the Secondary Endpoints

The analyses for the time to the first occurrence of secondary endpoints (1) time to the first occurrence of the composite of cardiovascular mortality, MI, or stroke; 2) time to all-cause

mortality) will be performed in the same manner as the primary analysis in Section 4.1, replacing the primary composite endpoint with secondary endpoints.

Competing risk of non-CV death or undetermined death will be taken into account for the secondary composite endpoint (time to the first occurrence of the composite of cardiovascular mortality, MI, or stroke). Follow-up will be censored at the time of non-CV or undetermined death if there is no prior composite event. For this endpoint, the treatment effect will be presented as a cause-specific hazard ratio.

All deaths post-randomization will be included in the secondary all-cause mortality endpoint. For this endpoint, a death date after withdrawal of consent or ICF expiration (obtained from public data sources) is considered an event.

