3.3.3 Sensitivity Analyses of the Secondary Outcomes

A sensitivity analysis is planned for the secondary composite endpoint where undetermined death will be classified as CV-death.

Another sensitivity analysis is planned for the secondary composite endpoint where cause of death is determined based on the best available data. Cause of death will first be determined based on the data from the CEC. If cause of death from the CEC is unavailable, cause of death will be determined from the CRF data. If cause of death from the CEC and CRF is unavailable, cause of death will be determined based on the NDI data.

A sensitivity analysis is planned for the secondary all-cause mortality endpoint where participants with no event will be censored at the last date that NDI results were assessed. The censoring date will be consistent for all participants without an event.

A sensitivity analysis will use Bayesian methods to estimate the secondary all-cause mortality outcome treatment effect posterior distribution. These analyses will be performed in an analogous manner as the Bayesian analysis of the primary outcome (section 3.2.2).

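### CV death/MI/stroke: Kaplan-Meier curves that censor non-CV and undetermined deaths would modestly overstate the cumulative incidence; Aalen-Johansen curves would not

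*Protocol*

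**What the plan says.** The display is set in the protocol and the censoring rule in the SAP, so the two must be read together.

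- **Protocol 9.6, Secondary Endpoint Analysis**, covers all time-to-event secondary endpoints: "Kaplan-Meier curves will be constructed to display the cumulative event rates of the treatment groups". CV death/MI/stroke is one of them (protocol 9.5.2). The protocol does not mention competing risks.
- **SAP 3.3.2** says the analyses of these endpoints "will be performed in the same manner as the primary analysis in Section 4.1". The SAP has no analysis under that number. The primary analysis is in 3.2.1, where "Kaplan Meier survival estimates will be constructed based on the time from randomization to the first" primary event.
- **SAP 3.3.2** then adds a rule for the CV composite alone: "Follow-up will be censored at the time of non-CV or undetermined death if there is no prior composite event". The only competing-risk output it names is a hazard ratio: "For this endpoint, the treatment effect will be presented as a cause-specific hazard ratio".
- **SAP 3.1.1, Table 3** states: "Non-CV death or undetermined cause of death is considered a competing risk". It assigns such a death its own event date and limits the censoring column to patients with neither the endpoint nor a competing event.
- **SAP 3.3.3** varies the cause of death: "A sensitivity analysis is planned for the secondary composite endpoint where undetermined death will be classified as CV-death". A second sensitivity analysis uses the best available cause. Neither changes how confirmed non-CV deaths are handled.

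Neither document names a cumulative incidence function, an Aalen-Johansen estimate or a Fine-Gray model.

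**The concern.** A patient who dies of another cause can no longer have an MI, a stroke or a CV death. Censoring at that death is correct for estimating the cause-specific hazard. Kaplan-Meier, however, treats a censored patient as still able to have the event later. One minus Kaplan-Meier therefore describes a setting in which the competing deaths do not occur, whereas the protocol says the curves are to show cumulative event rates.

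What is at stake is descriptive: the cumulative percentages by arm, and any absolute effect that a reader takes from them. The protocol summarises the predecessor trial partly by 5-year NNTs (section 2.1, Table 1), so readers may well use the new curves in that way.

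**Working it through.** **The plan's own figures.** The documents give no expected rate for CV death/MI/stroke, or for non-CV or undetermined death, so there is no planned figure to reproduce for this endpoint. The nearest design figure is the 282 primary events for 85% power at a hazard ratio of 0.70. The Schoenfeld formula gives 4 × (1.960 + 1.036)² / (ln 0.70)² ≈ 282.3, which agrees. That figure concerns the primary endpoint and has no bearing here.

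**Direction.** Let Λ₁ be the cumulative cause-specific hazard of the composite.

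- Cumulative incidence (the Aalen-Johansen target): ∫ S(u−) dΛ₁(u), where S is the probability of having had neither a composite event nor a competing death.
- One minus Kaplan-Meier with competing deaths censored: ∫ S₁(u−) dΛ₁(u), where S₁ ignores competing deaths.

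S₁ is never below S, and it is above S once a competing death has occurred. The second quantity is therefore larger in any arm where a competing death is followed by a later composite event in that arm.

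**Size.** Assume constant cause-specific hazards, a for the composite and b for competing death:

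- 1 − KM = 1 − exp(−a·t)
- CIF = a/(a+b) × [1 − exp(−(a+b)·t)]

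Inputs:

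- a = 3 to 6 and b = 0.5 to 4 per 100 patient-years (assumptions).
- t = 2.5 years, the follow-up in the power simulation of SAP Appendix I.
- t = 5 years, the maximum under SAP 1.1: "Patients will be followed for clinical events until the earlier of database lock or five years from randomization".

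| t (years) | a | b | 1 − KM | CIF | Excess (points) | Relative |
|---|---|---|---|---|---|---|
| 2.5 | 3 | 0.5 | 7.23% | 7.18% | 0.04 | 0.6% |
| 2.5 | 4.5 | 2 | 10.64% | 10.38% | 0.26 | 2.5% |
| 2.5 | 6 | 4 | 13.93% | 13.27% | 0.66 | 5.0% |
| 5 | 3 | 0.5 | 13.93% | 13.76% | 0.17 | 1.2% |
| 5 | 4.5 | 2 | 20.15% | 19.21% | 0.94 | 4.9% |
| 5 | 6 | 4 | 25.92% | 23.61% | 2.31 | 9.8% |

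The excess is computed before rounding. At each horizon the first and last rows are the smallest and largest excess in points over the assumed ranges.

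**Between arms, 5 years.** Assume a placebo rate a = 5 per 100 patient-years, a hazard ratio of 0.70 (so a = 3.5 on active) and b = 2 in both arms. The 0.70 is the design value for the primary endpoint, borrowed here as an assumption.

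- Placebo: 1 − exp(−0.25) = 22.12%; CIF = (0.05/0.07) × (1 − exp(−0.35)) = 21.09%.
- Active: 1 − exp(−0.175) = 16.05%; CIF = (0.035/0.055) × (1 − exp(−0.275)) = 15.30%.
- Risk difference: 22.12 − 16.05 = 6.07 points by Kaplan-Meier; 21.09 − 15.30 = 5.79 points by CIF.
- NNT: 100/6.07 ≈ 16.5 against 100/5.79 ≈ 17.3.

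The excess differs between arms (1.03 against 0.75 points) even with equal competing hazards. If chelation also multiplied the competing hazard by 0.70, the CIF risk difference would be 5.57 points while the Kaplan-Meier figure stayed at 6.07.

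**The case against.** **The display may be unspecified rather than wrong.** The Kaplan-Meier sentence in the protocol is generic and is right for all-cause mortality. SAP 3.3.2 does not repeat it, reaches the primary methods through a section number that does not exist, and says competing risk will be taken into account. Table 3 already codes competing deaths in the form that a cumulative incidence estimate needs. This has force: it would be wrong to conclude that the SAP overlooks competing risks. But the SAP puts nothing in place of the protocol's display, so someone following both documents would draw Kaplan-Meier curves with these deaths censored.

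**The planned inference is untouched.** A reader might infer that the treatment comparison is biased. The documents do not support that. Censoring competing deaths is the standard way to fit a cause-specific Cox model, and the hazard ratio and its third place in the testing hierarchy of SAP 3.2.1 stand. The primary endpoint and all-cause mortality count every death, so they have no such competing event.

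**Absolute effects are not planned outputs.** Neither document plans a risk difference or NNT for this endpoint. The NNTs in the protocol are results of the predecessor trial. This stands: any distortion of absolute benefit arises only if someone reads it from the curves. A reader might also assume that such an NNT would be too high. In the example it is too low, because the risk difference is too large.

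**The direction depends on how undetermined deaths are regarded.** The excess is measured against the endpoint as the SAP defines it, with undetermined deaths not counted as CV. At a = 4.5, b = 2 and 5 years, if 25% of the competing deaths were truly cardiovascular, the true incidence would be (0.05/0.065) × (1 − exp(−0.325)) = 21.34%, above the Kaplan-Meier 20.15%. That is a question of classification, which SAP 3.3.3 addresses separately.

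**Conclusion.** The point holds as a minor one about a descriptive display. Followed as written, the two documents give curves for CV death/MI/stroke that lie above the cumulative incidence of the endpoint as the SAP defines it.

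The direction does not depend on the assumed rates; the size does. Under constant hazards over the assumed ranges, the excess is about 0.04 to 0.7 points at 2.5 years and 0.2 to 2.3 points at 5 years. The 5-year figures apply at the maximum follow-up and should not be taken as typical of the whole curve. The documents support no claim of bias in the hypothesis test or in the trial's main conclusion.

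**What to change.** In SAP 3.3.2, and for this endpoint in protocol 9.6, state that curves and cumulative percentages for CV death/MI/stroke are Aalen-Johansen cumulative incidence estimates by arm, with non-CV and undetermined death as competing events. Keep the cause-specific Cox hazard ratio as the test, and keep Kaplan-Meier for all-cause mortality. In the sensitivity analysis that counts undetermined death as CV death, treat only non-CV death as competing. Correct the cross-reference in SAP 3.3.2 to section 3.2.1 at the same time. A separate hazard ratio for competing deaths is optional.

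The cost is a few sentences and a standard software option. The data are already coded in SAP Table 3, and alpha, power and the testing hierarchy do not change. The one visible consequence is that the reported percentages become slightly lower.

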### **Recurrent event analyses encompassing the overall event rate of endpoints for each patient.**

The components of this endpoint will include all-cause mortality, myocardial infarction, stroke, coronary revascularization, or hospitalization for unstable angina events. We plan to analyze this endpoint using two statistical techniques. The two approaches are:

- a) A generalization of the Cox model to handle recurrent events, developed by Anderson & Gill, with robust standard errors to account for heterogeneity.
- b) A marginal modeling approach developed by Wie, Lin, and Weissfeld.

The Anderson-Gill approach will be considered the primary analysis for the total number of all-cause mortality, myocardial infarction, stroke, coronary revascularization, or hospitalization for unstable angina events endpoint.

### **Exploratory Endpoints**

The comparison of costs will test mean direct medical costs incurred during the study (index infusion through end of follow-up). To account for staggered entry and incomplete follow-up, costs will be adjusted using the approach of Bang and Tsiatis. Statistical comparisons will be made using a normal approximation with standard errors

estimated using the bootstrap approach. The probability of differences in cost greater than thresholds of policy interest (such as \$1000, \$2000, or \$5000) will be calculated. Differences in cost by treatment group will be interpreted in the context of the trial clinical results, looking for both consistency and plausibility. Follow-up costs will be presented both overall and by category (e.g., inpatient readmission, outpatient procedures, concomitant medications, non-acute institutional care). Cumulative costs over the study period between treatment groups will be compared. Descriptive comparisons of cost according to clinical variables defining subgroups of interest will also be performed.

The analyses for toxic metals in blood and urine in the TACT2 population will proceed in three phases. First, we will evaluate if the chelation regimen has the effect on metal internal dose that we have postulated. To do this, we will compare body metal levels (lead in blood, pre-chelation urine lead and cadmium, and post-chelation urine lead and cadmium, in separate analyses) between active and placebo chelation groups at baseline and over the treatment phase of TACT2. Second, we will relate those levels to changes in the primary clinical endpoint (a composite of death from any cause, recurrent MI, stroke, coronary revascularization, or hospitalization for unstable angina) caused by chelation therapy relative to placebo. Finally, we will perform the exploratory analyses described below.

Over the 1-year period, we hypothesize there will be no change in metal levels in the placebo chelation group and significant reductions in the active chelation group. We also postulate these patterns of change in metal levels will explain, in a statistical sense, the clinical benefits we expect to see in TACT2 (the way LDL-cholesterol level lowering “explains” the benefits of statin therapy) using three complementary analytic approaches: 1] prespecified subgroup analyses (patients in the highest tertile of blood lead, urine cadmium, and post-chelation urine lead and cadmium at infusion 1, will show significantly larger treatment benefits (chelation vs. placebo) than patients with lower baseline levels), 2] landmark analyses (patients in the chelation arm with lower metal levels after 40 infusions/1 year of chelation will show significantly larger clinical benefits than patients with higher levels), and 3] we will apply causal inference modeling to evaluate whether the pattern of metal changes (lead in blood and cadmium in urine) in the chelation arm over the treatment period of TACT2 statistically “explains” the variation in clinical outcomes responsible for the hypothesized superiority of the chelation strategy.

We will also do exploratory analyses to examine the clinical implications of different patterns of metal removal over time on the benefits of chelation therapy (can metal levels be used as a biomarker to guide the number of chelation sessions needed to maximize clinical benefit from this therapy?) and to examine the effects of the oral multivitamin/mineral treatment regimen versus placebo vitamins on metal levels and on the effectiveness of chelation in reducing those levels (does the TACT2 vitamin regimen augment the ability of the chelation regimen to remove metals, or might there be a different mechanism of action altogether?). The latter case could be inferred if there were clinical benefits of OMVM, but no changes in lead and cadmium levels.

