### **1.2 Secondary Objectives**

The secondary objectives of TACT2 are to determine:

1. if the chelation-based strategy reduces the overall rate of occurrence of the events which define the primary TACT2 endpoint: all-cause mortality, myocardial infarction, stroke, coronary revascularization, or hospitalization for unstable angina events compared to placebo chelation strategy.
2. if the chelation-based strategy increases the time to the first occurrence of a combined secondary endpoint: cardiovascular mortality, myocardial infarction, or stroke compared to placebo chelation strategy.
3. if the chelation-based strategy increases the time to all-cause mortality compared to placebo chelation strategy.

Exploratory analyses, defined as those seeking to confirm a signal of benefit observed in TACT, or to develop mechanistic hypotheses for benefits of chelation expected in TACT2, include:

- i. Analysis of the primary endpoint in patients receiving OMVM compared with oral placebo
- ii. Analysis of the primary endpoint in patients receiving active chelation + active OMVM, compared with placebo chelation + placebo OMVM
- iii. Analysis of markers of severity of diabetes (fasting glucose, HbA1c, microalbuminuria) throughout the infusion regimen
- iv. Analyses of lead and cadmium in blood and urine to:
  - a. Compare the change in metal internal dose (blood lead and urine cadmium) in TACT2 participants, from infusion 1 to infusion 40 (or 1 year) in the active versus placebo infusion arms.
  - b. Evaluate whether higher screening metal internal dose (blood lead and urine cadmium) and the extent of depletion of those stores identify patients more likely to benefit from chelation.
- v. Collection of biospecimens for the constitution of a biorepository to support future

mechanistic work. Samples of blood (plasma and buffy coat) and urine will be stored at -80°C in a secured biorepository to ensure their availability for the evaluation of future hypotheses that will be guided by the results of the trial.

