### Preliminary data on metal excretion following a TACT2 infusion

A preliminary study measured metal excretion after one infusion of placebo, and one of active chelation. Twenty male participants (mean age 66, range 51 to 81) were recruited using the same criteria as in TACT (post-MI, age  $\geq 50$ , creatinine  $\leq 2.0$  mg/dL). Urinary concentrations of 20 toxic metals (Al, Sb, As, Ba, Be, Bi, Cd, Cs, Gd, Hg, Pb, Ni, Pd, Pt, Te, Tl, Th, Sn, W, U) normalized to creatinine excretion were measured at baseline, for 6 hours following a placebo infusion of 500 mL normal saline and 1.2% dextrose, and for 6 hours following a 3 gram edetate disodium-based infusion as used in TACT.

Following an edetate disodium-based TACT infusion, there was a striking increase in the urinary excretion of lead (mean 3,926% increase,  $P < 0.001$ ; Figure A), cadmium (739% increase,  $P < 0.001$ ; Figure B), and nickel (131% increase,  $P < 0.001$ ). There was also a modest increase in the urinary excretion of tin and thallium (30-40%;  $P < 0.05$ ). These preliminary data show that

Effect of Placebo or Edetate disodium-based infusion on urinary lead (A) and cadmium (B) excretion\*

\*Lines represent individual patient data points. Bar graphs are mean  $\pm$  SD of % change from baseline.

an edetate disodium-based infusion, identical to that used in TACT and proposed for TACT2, markedly increased excretion of lead and cadmium. Whether enhanced excretion of metals following repeated chelation infusions leads to a reduction in blood lead or pre-infusion urine cadmium (reflecting total body stores of each) is unknown, but will be identified by TACT2.

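### Two of the five exploratory metals comparisons, those on post-chelation urine lead and cadmium, cannot test the effect on internal dose if run as comparisons of level, as Protocol section 9.6 words them

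*Protocol*

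**What the plan says.** The metals analysis is exploratory. In Protocol section 9.6 (Exploratory Endpoints) its first phase has this aim: "we will evaluate if the chelation regimen has the effect on metal internal dose that we have postulated". The method is: "we will compare body metal levels (lead in blood, pre-chelation urine lead and cadmium, and post-chelation urine lead and cadmium, in separate analyses". The contrast is "between active and placebo chelation groups at baseline and over the treatment phase of TACT2". The next paragraph gives the expected result: "we hypothesize there will be no change in metal levels in the placebo chelation group and significant reductions in the active chelation group".

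Three other places bear on this.

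- Section 1.2, exploratory item iv.a: "Compare the change in metal internal dose (blood lead and urine cadmium) in TACT2 participants", from infusion 1 to infusion 40 or 1 year.
- Section 2.2, preliminary data: after one active infusion there was a "striking increase in the urinary excretion of lead (mean 3,926% increase" and likewise "cadmium (739% increase". The same text describes blood lead and pre-infusion urine cadmium as reflecting total body stores, and says that the effect of repeated infusions on them is not known.
- The paragraph closing section 1.2 gives post-infusion urine another role: predicting outcomes and benefit.

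SAP section 2.5 refers pre- and post-chelation metals to a separate SAP for the metals core laboratory, which is not among the documents.

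**The concern.** By section 5.1, the active infusion contains edetate and the placebo is saline with dextrose. A urine sample taken after the infusion therefore reflects, in the active arm only, what edetate mobilised that day. Comparing its level between arms asks whether edetate acutely raises urinary excretion, which the pilot has already answered. It does not ask whether stores have fallen. The comparison listed at baseline has the same fault, because a post-infusion sample at infusion 1 is taken after treatment has begun.

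What is at stake is interpretation. Two highly significant arm differences, in the direction opposite to the hypothesis, would be reported under the label of internal dose while carrying almost no information about it.

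**Working it through.** **1. The plan's own figure.** Section 9.2 claims at least 80% power for a difference of ¼ SD with 250 per group (two-sample t-test, two-sided 0.05). Power = Φ(d√(n/2) − 1.96) = Φ(0.25 × √125 − 1.96) = Φ(0.835) = 0.798; the exact noncentral t gives 0.797. The figure is reproduced to rounding. The chelation contrast pools two factorial groups, so it has about 500 per arm.

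**2. Size of the acute effect.** Fold = 1 + percent/100: lead 40.26, cadmium 8.39.

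**3. A bound that needs no SD.** The pilot had 20 men and reports P<0.001 for both metals. If that was a paired t-test (19 df), |t| ≥ 3.883 and d ≥ 3.883/√20 = 0.868. Used between arms:

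- 250 per arm: Φ(0.868 × 11.18 − 1.96) = Φ(7.74), above 0.9999; higher still with 500.
- A paired d is not a between-arm d; under equal variances the latter is d√(2(1 − ρ)). Halving it to 0.434 corresponds to ρ = 0.875. Power is then Φ(4.85 − 1.96) = 0.998 with 250 per arm and above 0.9999 with 500.

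**4. Log scale.** The documents give no SD, so log SD 0.5 to 2.0 is assumed. d = ln(fold)/SD.

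| Metal | ln(fold) | d at SD 0.5 | d at SD 2.0 | Power, 250 or 500 per arm |
|---|---|---|---|---|
| Lead | 3.695 | 7.4 | 1.8 | 1.000 |
| Cadmium | 2.127 | 4.3 | 1.1 | 1.000 |

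The pilot figures are arithmetic means, so the geometric fold is probably smaller. With an assumed log SD of 1.0 for the ratio, cadmium becomes 8.39 × e^(−0.5) = 5.09 and ln = 1.627. At SD 2.0, d = 0.81 and power with 250 per arm is Φ(9.1 − 1.96), still about 1.

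**5. Simulation, stores unchanged.** 1,000 trials per scenario; 250 or 500 per arm; assumed log-scale SD components from (0.5, 0.5) to (1.5, 1.0); 0%, 40% or 70% of patients not infused at the late visit.

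- Post-chelation level at infusion 40: rejects in about 100% of trials, always with active higher. It is still 100% with 40% not infused. The lowest cadmium result is 95% (70% not infused, 250 per arm, widest SDs).
- Post-chelation level at infusion 1: rejects in 100%.
- Pre-infusion level at infusion 40, or change from infusion 1: about 4–6%.
- Change in post-chelation urine from infusion 1 to 40, among those infused at both: about 4–7%.

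**6. Simulation, stores halved** (500 per arm, all infused). The post-chelation level still rejects in 100% with active higher, the wrong sign for a real reduction. The pre-infusion contrasts detect the fall in 100%.

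**7. Fall needed before the arms look equal.** 1 − 1/fold: 97.5% (lead) and 88.1% (cadmium) if the pilot means are taken as geometric ratios. With the adjustment in step 4, lead is 40.26 × e^(−0.5) = 24.4, giving 95.9%, and cadmium is 5.09, giving 80.4%. These thresholds are indicative only.

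**The case against.** The strongest reply is that a comparison of change is meant. Item iv.a says change, the hypothesis in section 9.6 is stated as change over a year, and no test, model or time point is named. A change contrast would be sound, as step 5 shows. That stands as a possible intention. But the sentence that specifies the analysis speaks of levels between groups and expressly includes baseline, so the text needs an edit either way. The unseen metals SAP may already define the contrast properly.

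A reader might also infer more than the documents support:

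- *That the whole first phase fails.* It does not. The five measures are analysed separately; blood lead and both pre-chelation urine measures remain valid, including both measures in iv.a.
- *That a rejection rate near 100% means a false claim of depletion.* The rejection runs against the hypothesis, so no such claim could follow.
- *That the fault spreads to the later mechanistic work.* The second phase does refer back to these levels. However, the causal modelling names lead in blood and cadmium in urine, and the landmark analysis is within the chelation arm, where a between-arm offset does not enter. Carry-forward to these is not shown.
- *That the protocol says only blood lead and pre-infusion urine cadmium reflect stores.* It says that these two do; it does not exclude others.

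**Conclusion.** The concern holds for two of five exploratory comparisons, and only if they are run as comparisons of level, which is how section 9.6 is worded. In that form they would almost surely show the active arm higher whether or not body stores change, and so cannot test the postulated reduction. Section 9.6 is also out of line here with item iv.a, the closing paragraph of section 1.2 and the pilot text.

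The conclusion rests on three assumptions: the SD ranges shown, little or no rise after placebo (the pilot's value is in a figure not shown), and a post-infusion collection similar to the pilot's 6 hours. Near-certain rejection survives wide variation in the first. The point is minor: it has no effect on the primary, secondary or safety conclusions.

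**What to change.** In Protocol section 9.6, and in the metals SAP if it says the same:

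1. Base the arm comparison of internal dose on change from the infusion-1 pre-infusion sample in blood lead and pre-infusion urine cadmium, as in iv.a. Pre-infusion urine lead, which iv.a does not list, can be kept as an additional measure.
2. Take post-chelation urine out of the list of body metal levels. Analyse it separately as mobilised excretion, by change from infusion 1 to infusion 40, within the active arm or as arm-by-time, and not by its level between arms. State that this uses only patients infused at both visits.

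The cost is a sentence or two. Metals sampling is already scheduled at infusions 1, 5, 20 and 40, so no new samples are needed. The only downside is that one listed exploratory comparison is relabelled.

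The replacement test keeps useful power under assumed values. For a 20% fall with 400 per arm and an SD of log change of 0.8, z = −ln(0.8)/(0.8 × √(2/400)) = 3.94 and power = Φ(3.94 − 1.96), about 0.98. With SD 1.2, z = 2.63 and power is about 0.75.
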